## **Study Protocol**

### **Effects on the Olfactory Epithelium and the Olfactory Nerve from Exposure to Diesel Exhaust**

#### **Scientific Research Question**

The overall goal of this research project is to study and deepen our understanding of the health effects associated with exposure to air pollution generated by the combustion of diesel, focusing on the nervous system.

#### **Specific aim:**

- To study the oxidative and inflammatory effects of exposure to diesel exhaust on the respiratory epithelium and the olfactory nerve in healthy individuals. Additionally, the study aims to determine whether these exposures result in measurable effects on the sense of smell and cognitive ability.

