## **Project Description**

The studies will be conducted using our well-established techniques and methods. Exposure to controlled levels of motor exhaust from diesel fuel has been conducted for more than two decades, and in recent years we have also developed a collaboration with Associate [name] group at the Thermochemical Energy Conversion Laboratory (TEC-Lab) at Umeå University. This offers a unique opportunity to study under different combustion conditions.

**Hypothesis:** Diesel exhaust cause cell dysfunction in the olfactory system secondary to mitochondrial dysfunction and oxidative stress. Additionally, we hypothesize that these exposures result in measurable effects on the sense of smell and cognitive ability.

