**Hypothesis:**

Diesel exhaust gases cause cell dysfunction in the olfactory system secondary to mitochondrial dysfunction and oxidative stress. The hypothesis also includes studying whether exposures lead to measurable effects on the sense of smell and cognitive abilities.

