### Olfactory Epithelium Biopsy

After local anesthesia with Xylocain following exposure, a small biopsy of the nasal mucosa will be taken by a specialist doctor. Material from the nasal biopsies will be used both for culture experiments and for later analyses, including PCR analysis after freezing at -80°C, and will be sent to our collaborators, [name] and [name] at the University of Eastern Finland. Nasal mucosa biopsies have been performed previously at the ENT department at Umeå University following ethical approval. Complication risks are virtually nonexistent, but there may be minor discomfort or slight nasal bleeding, which can be easily stopped using a compress applied to the biopsy site. ENT doctors are experienced in managing nasal bleeding. Biopsy sampling will be randomized between the left and right sides across two exposure sessions, with the contralateral biopsy taken after the second exposure.

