### In-Vitro Studies and Biomarker Analysis

Effects at the cellular level of exposure to air pollution will be studied in olfactory epithelial cells using in-vitro tests at the University of Kuopio, Finland. RNA sequencing and DNA methylation will be conducted to identify biomarkers for acute exposure to air pollutants at the Institute of Experimental Medicine, Czech Academy of Science, Czech Republic.

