### Blood Tests

Blood samples will be taken before exposure and before olfactory epithelium biopsies. These will be analyzed for cell count, inflammation markers, and lymphocyte subtyping using flow cytometry. A maximum of 100 ml of blood will be drawn during each exposure.

The effects of exposure to air pollution at the cellular level will be studied in monocytes from peripheral blood using in-vitro tests. Further analyses, including PCR (polymerase chain reaction), will be conducted for the APOE gene, a genetic factor that can influence sensitivity to air pollution. These analyses will be performed at Kuopio University, Finland.

RNA sequencing and DNA methylation will also be conducted to identify biomarkers for acute exposure to air pollution at the Institute of Experimental Medicine, Czech Academy of Science, Czech Republic.

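### Does naming the respiratory epithelium in the aim, with no named oxidative or mitochondrial readout, mean the trial cannot answer its own question?

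*Protocol*

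**What the plan says.** The specific aim has two parts. The first is "To study the oxidative and inflammatory effects of exposure to diesel exhaust on the respiratory epithelium and the olfactory nerve in healthy individuals". The second is that "the study aims to determine whether these exposures result in measurable effects on the sense of smell and cognitive ability".

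The title is "Effects on the Olfactory Epithelium and the Olfactory Nerve from Exposure to Diesel Exhaust". The hypothesis appears twice in nearly the same words, under Project Description ("Diesel exhaust cause cell dysfunction in the olfactory system secondary to mitochondrial dysfunction and oxidative stress") and again under its own heading ("Diesel exhaust gases cause cell dysfunction in the olfactory system secondary to mitochondrial dysfunction and oxidative stress").

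Study Design calls the specimen a mucosal biopsy of the olfactory epithelium. The section headed Olfactory Epithelium Biopsy says that "a small biopsy of the nasal mucosa will be taken by a specialist doctor", and assigns the material to culture and to later analyses that include PCR. In-Vitro Studies and Biomarker Analysis plans cell-level tests in olfactory epithelial cells and adds that "RNA sequencing and DNA methylation will be conducted to identify biomarkers for acute exposure to air pollutants". On blood, the Blood Tests section says "These will be analyzed for cell count, inflammation markers, and lymphocyte subtyping using flow cytometry", and it also plans in-vitro tests on monocytes, APOE analysis, RNA sequencing and methylation. Smell and cognition each have a named instrument.

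**The concern.** Respiratory and olfactory epithelium are different tissues. A trial named after one should not state its aim in terms of the other, and the broader term nasal mucosa in the biopsy procedure does not settle which is meant. If the two biopsies from one participant came from different tissue types, the diesel-minus-air difference for that person would largely reflect tissue and not exposure.

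The second strand is the mechanism. The hypothesis is specific, but the sequencing is described as a search for biomarkers. If nothing is fixed in advance, the mechanistic claim could end up resting on whichever genes happened to stand out. The stake would be the loss of a confirmatory test of the central hypothesis.

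**Working it through.** The protocol gives no power, effect size or variance, so there is no figure of its own to reproduce. The check is mainly a comparison of sections, followed by the arithmetic behind the feared consequences.

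**1. Tissue named in each place**

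| Place in protocol | Tissue |
|---|---|
| Title | olfactory epithelium and nerve |
| Specific aim | respiratory epithelium and olfactory nerve |
| Hypothesis (both statements) | olfactory system |
| Study Design | olfactory epithelium |
| Olfactory Epithelium Biopsy | olfactory in the heading, nasal mucosa in the text |
| In-Vitro Studies and Biomarker Analysis | olfactory epithelial cells |
| Blood Tests (timing of samples) | olfactory epithelium biopsy |

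Only the aim differs, and it too names the olfactory nerve. Olfactory epithelium is part of the nasal mucosa, so the wording of the biopsy procedure is broader than its heading but does not contradict it.

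**2. Readout for each element of the aim and hypothesis**

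- Smell: Sniffin' Sticks threshold, named.
- Cognition: Letter Digit Substitution Test, named.
- Inflammation: blood inflammation markers and lymphocyte subtypes, named. No tissue marker is named.
- Oxidative stress and mitochondrial function: no assay named. Culture, PCR, cell-level in-vitro tests and RNA sequencing are planned and can carry them.

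The accurate statement is therefore that these readouts are not specified, not that the data cannot address them.

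**3. What mixed tissue would do.** The protocol gives no rate at which a biopsy misses olfactory tissue. Assume a probability q per biopsy, independent between sides and unrelated to exposure. Pairs olfactory on both sides number 40(1−q)²:

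- q = 0.10: 40 × 0.81 = 32.4
- q = 0.20: 40 × 0.64 = 25.6
- q = 0.40: 40 × 0.36 = 14.4

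Mixed pairs number 40 × 2q(1−q) = 7.2, 12.8 and 19.2.

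Now let the two tissues differ by Δ on some measure, and let diesel shift olfactory tissue by δ and respiratory tissue not at all. The expected diesel-minus-air difference is (1−q)δ + (qΔ − qΔ) = (1−q)δ. The tissue term cancels because a miss is equally likely under either exposure. With no exposure effect (δ = 0) the expected difference is zero, whatever Δ is. With an effect, it is diluted to 0.9, 0.8 or 0.6 of δ, and the mixed pairs add variance 2q(1−q)Δ². So a single pair can mislead, but the group comparison is not given a false effect.

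**4. What testing would cost.** For a paired comparison with 80% power, two-sided, using the noncentral t distribution (effects in SD of the paired difference):

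- 40 pairs, one score at 5%: 0.454 SD
- 40 pairs, two scores at 2.5% each: 0.504 SD
- 40 pairs, one gene among 10,000 to 20,000 (assumed) with Bonferroni: 0.986 to 1.022 SD

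The gap between 0.45–0.50 and about 1.0 SD shows the value of naming a pathway in advance. It does not show a fault in this protocol, which fixes neither a gene-by-gene Bonferroni rule nor unadjusted testing.

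**5. What a marker-confirmed main analysis would do.** With two scores at 2.5% each, 32, 26 or 14 confirmed pairs would detect 0.57, 0.64 or 0.91 SD, against 0.50 SD with all 40. The larger difficulty is selection. Olfactory marker genes would be measured after exposure, and the hypothesis is that diesel damages olfactory cells. If that damage lowers the markers, the most affected diesel samples are the ones removed, and the estimated effect shrinks. Assessing the markers blind to exposure does not prevent this.

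**The case for a change.** The best case for a change is that what to measure for a central hypothesis belongs in the protocol, and only how to analyse it belongs in an analysis plan. The protocol names instruments for smell and cognition, so it works at that level of detail elsewhere and is silent on the mechanism it puts first. An analysis plan would not normally correct a misnamed tissue in an aim either. And if the mechanistic readouts were picked after the sequencing results were seen, the confirmatory test would be lost.

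Part of this stands. The aim's wording is wrong against the rest of the document. The mechanistic readouts are unnamed, and the in-vitro section does not say outright whether the sequenced material is the biopsy or cultured cells.

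It does not carry a change to the plan. Every operational section directs the team to olfactory tissue, so the slip misleads nobody about what to sample. Gene sets, multiplicity rules and the split between confirmatory and exploratory analyses are commonly left to an analysis plan, and this trial's may exist. The protocol states that samples are coded and data handled blind, so a sensible analyst can settle the readouts before the codes are opened. Because it is not certain that the biopsy itself is sequenced, the claim that pathway scores would need no new assay is also unproven. Preferring transcript scores to the planned cell tests would be a matter of choice.

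**Conclusion.** The concern does not call for a change. The tissue mismatch is a clerical slip confined to one phrase of the aim, with no effect on sampling, measurement or comparison. The unnamed oxidative and mitochondrial readouts are a gap that the planned assays can fill and that analysts would ordinarily close before unblinding. Tissue misclassification has no rate in the document to support it. At assumed rates of 10% to 40% it would dilute an effect to between 0.9 and 0.6 of its size and add noise, without creating a false one.

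This rests on three assumptions: each participant receives both exposures, as the biopsy section's two sessions imply; misses are unrelated to exposure, which randomising exposure and side supports; and the mechanistic readouts are settled before the codes are opened. If they were instead chosen after the results were seen, any mechanistic finding should be read as exploratory.

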#### **Background**

UNICEF recently published a report highlighting the health effects of air pollution from a global perspective, with a particular focus on the situation for children. It is estimated that air pollution causes approximately 7 million deaths each year globally, with around 600,000 of these deaths being children under 5 years old. Indoor and outdoor air pollution are the 3rd and 9th leading causes of death, respectively, contributing to about 3.5 million premature deaths in 2010.

The Swedish Environmental Research Institute IVL has estimated the Swedish healthcare and societal costs due to the negative impacts of air pollution on heart attacks, strokes, asthma, chronic obstructive pulmonary disease (COPD), and pneumonia at 42 billion SEK annually.

Living in areas with high levels of air pollution is a risk factor for diseases of the central nervous system, including Alzheimer's disease (AD) and cognitive impairment in the elderly, Parkinson's disease, and stroke.

It has also been demonstrated in people living in highly polluted urban areas that fine particles (PM2.5) have been found in the brain, showing that iron particles (magnetite) can be translocated to the brain. The entry point is the olfactory nerve, where particles can enter directly without having to penetrate the blood-brain barrier to reach the brain. It is primarily ultrafine particles (with an aerodynamic diameter  $<100-200$  nm) that can enter through the olfactory nerve via inhalation. Particles of this size range originate from both motor exhausts and biomass combustion, depending on the combustion technique.

The olfactory nerve area is thus an important region of interest for understanding how particulate matter (PM) damages the brain. Interestingly, olfactory dysfunction has been reported in elderly women exposed to high levels of PM (19). It is critical that this possible entry route into the central nervous system is studied in detail to better understand the health effects of PM exposure in humans and to identify potential new biomarkers for air pollution effects.

Dementia is a major cause of morbidity and mortality worldwide. By 2050, the number of Alzheimer's disease (AD) patients is expected to rise to over 130 million, up from 47 million today. In a study from northern Sweden, researchers (Forsberg et al.) demonstrated that exposure to traffic-related air pollutants may be a risk factor for the development of vascular dementia and Alzheimer's disease. Alzheimer's disease is the most common neurodegenerative disease, and there is currently no cure. Current medications only alleviate symptoms. Neuropathological changes in AD include the deposition of protein aggregates, neuroinflammation, and oxidative stress. Despite the clinical evidence that olfactory dysfunction precedes AD-associated cognitive decline by several decades, the significance of air pollution effects on the olfactory area has not been studied in human trials.

Lipophilic particles such as diesel exhaust have been shown in animal studies to penetrate the brain via the olfactory epithelium and the olfactory nerve, causing neurological effects. Particles can, depending on the hydrocarbon profile on their surface and protein interactions, be transported along neurons, leading to post-translational neurogenic effects. This is likely not unique to the central nervous system but may also occur in the airways. We have previously demonstrated CNS effects using quantitative EEG analysis, which is consistent with increasing epidemiological reports of neurogenic impacts of air pollution.

Our colleagues in Finland have established a new physiologically relevant human model of olfactory epithelium from healthy non-demented controls and Alzheimer's patients that can be used to study the effects of air pollution. By examining the acute effects on the olfactory nerve following exposure to diesel exhaust, this is a crucial step in advancing knowledge about the health effects of these two major contributors to PM.

## **Inclusion Criteria and Population**

Healthy non-smoking participants aged 20-70 years with an equal gender distribution will be recruited.

The participants will be examined regarding clinical status, lung function, prick test, ECG, blood status, bleeding status, Na+, K+, and creatinine.

## **Exclusion Criteria**

1. Allergic rhinitis
2. Asthma
3. Diabetes mellitus
4. Renal or liver failure
5. Angina or previous ventricular arrhythmia
6. Systolic blood pressure >190 mmHg or <100 mmHg
7. Previous blood disorders
8. Blood donation within the past three months

9. Previous or ongoing tobacco smoking and exposure to air pollution in the workplace
10. Lack of informed consent

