**ResearchParticipants:**

Forty healthy, non-smoking individuals aged 20-70 years will be included. Strict inclusion and exclusion criteria will be applied based on a medical assessment as outlined above.

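### Do the loose wording of exclusion 9 and the lack of a smell-loss criterion call for a change to eligibility?

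*Protocol*

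**What the plan says.** The Exclusion Criteria list ten items. Item 9 is "Previous or ongoing tobacco smoking and exposure to air pollution in the workplace". Other items that pair two conditions use a different conjunction, for example "Renal or liver failure" and "Angina or previous ventricular arrhythmia".

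Inclusion Criteria and Population states: "Healthy non-smoking participants aged 20-70 years with an equal gender distribution will be recruited". The same section lists the screening examinations. They include a general check of clinical status but no smell test. The research participants section repeats the healthy, non-smoking requirement for the forty people and adds: "Strict inclusion and exclusion criteria will be applied based on a medical assessment as outlined above".

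The only nasal condition excluded is allergic rhinitis. SARS-CoV-2 is tested before each exposure session.

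On smell, the Specific aim says that "the study aims to determine whether these exposures result in measurable effects on the sense of smell and cognitive ability". Olfactory Testing measures this as an n-butanol detection threshold over 16 concentrations.

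**The concern.** Two things look wrong at first.

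**Item 9.** Items 4 to 6 use 'or' where one condition is enough, and item 9 uses 'and'. A literal reader could conclude that only people with both a smoking history and workplace exposure are kept out. Screeners might then differ, and people with long-term pollution exposure could enter a study of a single hour's exposure.

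**Smell loss.** A participant who cannot detect even the strongest pen has no room to worsen, so that person adds nothing to the smell comparison. The Background suggests that such people exist: it notes that "olfactory dysfunction has been reported in elderly women exposed to high levels of PM" and that "olfactory dysfunction precedes AD-associated cognitive decline by several decades". With ages up to 70, some enrolled participants could have impaired smell, and a real effect of diesel exhaust on smell could be missed.

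**Working it through.** **1. Who depends on the reading of item 9.** Cross smoking history (ever or never) with workplace exposure (yes or no), which gives four combinations.

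| Smoking history | Workplace exposure | Either excludes | Both needed |
|---|---|---|---|
| Ever | Yes | Excluded | Excluded |
| Ever | No | Excluded | Admitted |
| Never | Yes | Excluded | Admitted |
| Never | No | Admitted | Admitted |

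The readings differ in two combinations. In the second row, current smokers are still barred by the non-smoking requirement, so only ex-smokers are in doubt there. The disputed groups are therefore ex-smokers without workplace exposure and never-smokers exposed at work.

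**2. Which reading fits the text.** Item 9 names ongoing as well as previous smoking. If both conditions were needed, the word 'ongoing' would do no work, because current smokers are already ineligible. If either condition excludes, item 9 agrees with the non-smoking requirement and extends it to ex-smokers. Inside the item, 'or' joins two variants of smoking and 'and' adds a second excluded group, which is ordinary list usage. The contrast with the other items is weak evidence. Item 6 gives an upper and a lower blood-pressure limit and has to say 'or', since nobody can meet both. That leaves items 4 and 5.

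**3. Whether smell loss biases the comparison.** Study Design has forty people exposed to diesel exhaust and filtered air, randomised. Olfactory Epithelium Biopsy describes two sessions, with the opposite side biopsied after the second. Each person therefore appears to serve as their own control, and a stable smell deficit is present under both exposures. Study Design also speaks of two groups. Even if the arms were parallel, randomisation would spread the deficit without favouring one exposure. What remains is lost sensitivity.

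**4. How much sensitivity, for scale only.** The protocol gives no effect size, standard deviation, significance level, power or share with smell loss, so there is no stated figure to reproduce. The only documented input is n = 40. Assumed: a paired t-test at two-sided 5%, and a true effect that 40 pairs detect with 80% power, which is d/s = 0.454 standard deviations of the paired difference.

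Let a share f have no measurable smell. Their mean difference is zero and their variance is r·s². Then:

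- mean difference = (1 − f)·d
- variance = s²·[(1 − f) + f·r + f(1 − f)(d/s)²]
- effective n = 40(1 − f)² / [(1 − f) + f·r + f(1 − f)(d/s)²]

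r = 0 means these people give near-zero differences. r = 1 means they give full guessing noise.

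| f (assumed) | r | Denominator | Effective n | Power |
|---|---|---|---|---|
| 5% (2 of 40) | 0 | 0.95 + 0 + 0.0098 = 0.9598 | 36.1 / 0.9598 = 37.6 | 77.5% |
| 5% | 1 | 0.95 + 0.05 + 0.0098 = 1.0098 | 36.1 / 1.0098 = 35.8 | 75.4% |
| 10% (4 of 40) | 0 | 0.90 + 0 + 0.0186 = 0.9186 | 32.4 / 0.9186 = 35.3 | 74.9% |
| 10% | 1 | 0.90 + 0.10 + 0.0186 = 1.0186 | 32.4 / 1.0186 = 31.8 | 70.5% |

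The loss is 2.5 to 4.6 points at 5%, and 5.1 to 9.5 points at 10%.

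**5. Whether those shares are plausible.** The two Background statements concern elderly women with high particulate exposure and people who later develop Alzheimer's disease. Neither gives a rate for healthy people aged 20 to 70. Both speak of dysfunction, whereas the table models complete absence of smell. Someone with partial loss may still worsen on a 16-step scale.

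**6. What an added criterion would recover.** A history question finds only smell loss that the person has noticed. An examination of healthy volunteers for clinical status would probably find that already. Unnoticed loss would still get through, so most of the loss in the table might not be recovered.

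**The case for a change.** The best case for a change is that eligibility belongs in the protocol and no analysis plan will supply it. Screeners apply the text, so if either condition is meant to exclude, the text should say so. A medical assessment of healthy people leaves known smell loss to the investigator's discretion, while the protocol promises strict criteria. Smell is a stated aim, the sample is only forty, and the remedy is a wording edit plus one question at a visit already planned.

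The facts in this case stand. Item 9 is loosely worded, and no written criterion names smell loss. The arithmetic is also sound under its assumptions. What does not follow is that a result is at risk. The power figures concern people with no measurable smell. They say nothing about ex-smokers or workplace-exposed never-smokers, for whom no effect on any outcome has been shown. Counting combinations in a table does not tell us how many such people would enroll. Low cost alone does not make an edit necessary.

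**Conclusion.** No change is needed. Exclusion 9 is a drafting looseness that screeners would very likely resolve correctly: either condition excludes. If some did not, the people admitted would be ex-smokers and workplace-exposed never-smokers, each compared with themselves. The missing smell-loss criterion is a gap that the healthy-participant requirement and the clinical examination probably cover for known loss.

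Any residual cost falls on the sensitivity of one outcome. The biopsy, blood and cognitive comparisons are untouched. Its size cannot be taken from the protocol; the illustration gives about 2 to 5 power points at an assumed 5% share and about 5 to 10 at 10%, from an assumed 80% start. The judgement that there is no bias rests on randomisation and on the two-session design implied by the biopsy section.

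The sponsor may choose to split item 9 for tidiness or to record known smell loss at the medical assessment. Either is optional, and the diesel versus filtered-air conclusion stays sound without them.
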